Social determinants (e.g., social and built environments) have an important impact on health outcomes.⁸⁻¹⁰ Yet these factors are often ignored at the point-of-care. Providers lack time and patient- and community-specific data necessary to provide tailored, evidence-based care within their routine practice.¹¹ Interactive Behavior Change Technology enables a data-driven, patient-centered approach to prevention that has potential to be scaled across clinics, populations and disease types.¹² Increasing awareness of community resources (*e.g.*, parks, community centers, farmer's markets) has resulted in weight loss in children.¹³ Yet, an EHR-compatible tool has not been used to provide adolescents with patient-centered, community resources at the clinic visit. This research will fill this critical gap with our novel Patient-centered Real-timE interVENTion (PREVENT) tool.

Significance:

Only 4% of adolescents meet the American Heart Association's Life Simple 7 CVH metrics (*e.g.*, obesity, physical activity and healthy food intake) that are important for preventing cardiovascular disease, and this percentage was even lower among those of low-SES. ^{3,7,14-16} Increasing physical activity and healthy food intake using effective interventions that are scalable, sustainable, and elicit equitable change across populations are necessary to address the approximately 19% of adolescents with obesity.⁷

Primary care physicians reach a large number of adolescents and have the potential to reduce poor CVH during well-child visits.¹⁷ Yet, providers lack the training and time to identify and address health behavior issues.^{18,19} Evidence-based behavior change has not been adopted into practice, despite technological advances (*e.g.,* Interactive Behavior Change Technology) that can facilitate this with little burden.²⁰

To achieve health equity, behavior change interventions should address the environment surrounding at-risk youth.²¹ The ability to be physically active and improve healthy food intake is dependent on the built environment²²⁻²⁴ and/or knowledge of existing resources and infrastructure (*e.g.,* transportation) to access resources, particularly for low-SES populations.²⁵⁻²⁸ Linking youth and their families to resources (*e.g.,* parks, community centers, healthy food outlets) is a practice that aligns with the American Academy of Pediatrics recommendations for community pediatricians²⁹ and the Chronic Care Model.³⁰ Several primary care-based interventions have linked patients to community resources and show promising weight loss in adults and children.^{13,31,32} Yet, taking such

interventions, coupled with evidence-based behavior change strategies and integrating them into a clinical practice workflow has not been tested in adolescents.

1.0 Study Aims:

The proposed research will test the feasibility of administering PREVENT, a pragmatic, equitable approach to prevention, in the Late Effects Clinic at St. Louis Children's Hospital and the St. Louis Children's Specialty Care Center (CSCC) to prepare for subsequent implementation and dissemination. The central hypothesis is that PREVENT will improve patients' attitudes toward behavior change recommendations, to better adhere to recommendations and improve CVH.

Aim 1. Determine barriers to current and future implementation of the PREVENT tool (e.g., usability, acceptability, motivation, workflow compatibility) to inform adoption and maintenance.

Aim 2. Assess the impact of the PREVENT tool on patients' attitudes toward behavior change recommendations and on the control of CVH risk factors (*e.g.*, body mass index [BMI], physical activity and healthy food intake).

2.0 Summary of Study Plan

Fifty adolescents aged 12 to 19 years at risk for poor CVH (BMI \geq 85th percentile) will be recruited over a 9-month period (**Table 1**) from the Late Effects Clinic and randomized to intervention or wait-list control (**Figure 1**). Provider's and patient's perceptions of barriers to implementation and maintenance of PREVENT (*e.g.*, usability, acceptability, motivation for use, workflow compatibility) will be

Year	1		2					
Quarter	1	2	3	4	1	2	3	4
Recruit Advisory Board								
Develop Manual of Procedures								
IRB Approval								
Train Study Staff								
Advisory Board Bi-Annually								
Recruit								
PREVENT Feasibility Study								
Data Analysis								
Manuscript Development								
Refine PREVENT Tool								
R01 Submission								

examined using: 1) surveys administered to all providers at clinic; 2) semi-structured interviews with 5-10 diverse providers (*e.g.*, physicians, nurses, clinic staff, clinical research associates); and 3) two focus groups, one with patients (n=10) and one with parents (n=10) (**Aim 1**). These evaluations will be guided by RE-AIM³³ and administered following the intervention period. Implementation (*e.g.*, intervention delivery, fidelity, time

FOR IRB USE ONLY \$STAMP_IRB_ID \$STAMP_APPRV_DT \$STAMP_REL_DT \$STAMP_EXP_DT

of use) will be examined using direct observation and audio recordings of 15 providerpatient interactions while using PREVENT. Patient attitudes toward behavior change recommendations and risk factors (BMI z-score, cholesterol, blood pressure, physical activity and food intake) will be measured using surveys, physical activity tracking devices (accelerometers) and EHR-data extraction at baseline and 3-months (**Aim 2**). An advisory board will be established and meet bi-annually to provide adolescent (n=5), parent (n=5) and provider (n=5) perspectives on study implementation and inform revisions to PREVENT.

Key dates (Table 1).

- Provider training: October 2020-January 2021
- Patient recruitment: February 2021- April 2021
- PREVENT feasibility study: January 2021-September 2021

3.0 Study Population

We will evaluate the PREVENT tool at the Late Effects Clinic at St. Louis Children's Hospital and the CSCC with:

- 1. Fifty adolescents aged 12 to 19 years at risk for poor CVH (BMI $\ge 85^{th}$ percentile) and their parents.
- 2. All providers and clinic staff (physicians, nurses, clinic staff, clinic research associates) who were involved with the implementation of PREVENT at the Late Effects Clinic.

3.1 Patient eligibility criteria.

- 1. Adolescents 12 to 19 years
- 2. Prior diagnosis of pediatric cancer (diagnosed <21 years of age).
- 3. Not receiving active therapy for their cancer
- 4. Receiving care from the Pediatric Hematology/Oncology staff and physicians at St. Louis Children's Hospital or the St. Louis Children's Specialty Care Center
- 5. At risk for poor CVH (BMI $\ge 85^{\text{th}}$ percentile)

3.2 Provider eligibility criteria. All providers and clinic staff (physicians, nurses, clinic staff, clinic research associates) in the Pediatric Hematology/Oncology program at St. Louis Children's Hospital and the CSCC.

3.3 Parent eligibility criteria. A parent or legal guardian of a study participant. The parent or legal guardian must have been present at the clinic visit in which the PREVENT tool was administered to the study participant.

4.0 Study Procedures

4.1 Recruitment

4.1.1 Patient recruitment. A designee at the clinic will query the clinic's EHR using inclusion/ exclusion criteria to develop a list of eligible patients with contact

FOR IRB USE ONLY \$STAMP_IRB_ID \$STAMP_APPRV_DT \$STAMP_REL_DT \$STAMP_EXP_DT

information (parent contact information will be used for patients ≤18 years). Study staff will mail a letter informing them of the study and then recruit via telephone. The letter will be addressed to the parent/guardian if the patient is ≤18 years of age; otherwise, the letter will be addressed to the patient. The recruiter will describe the study and administer a phone-based screener. If interested and eligible, patients will be consented and enrolled.

A subset of patients (n=10) and their parent (n=10) will be recruited to participate in a focus group discussions following the intervention period. Recruitment will leverage contact information collected during the feasibility trial to recruit over the phone or email.

4.1.2 Provider recruitment. The study team will present the study and review the consent document at the clinic's monthly research meeting and allow time for providers to ask questions. If an eligible provider is not in attendance, the provider will be contacted via email to schedule an individual meeting conducted over zoom to explain the study and review the consent document.

4.2 Enrollment and Consent

4.2.1 Patient enrollment. If patient is interested, the consent form will be reviewed over the phone. Adequate time will be allotted to allow the patient to ask any questions. Additionally, the patient may use the contact information provided on the consent document to follow-up with additional questions prior to completing the consent. If the patient is 18 years or younger, we will ensure that the parent is on the phone while we review the consent document. If the parent is not available, we will call back to discuss the consent form. Following this conversation, an electronic consent (developed in REDCap with guidance from the ICTS mHealth Research Core) will be emailed. The study team will send a test email in a secure manner (i.e., [secure] in subject line) prior to sending consent to verify the participant's identify. The email will instruct the participant to send all information as a response to this thread and not to remove the "[secure]" from the subject line. All future email correspondence will follow this protocol. If the patient is 18 years or younger, the parent and patient will be required to complete the consent document. If the patient is at least 19 years of age, the parent is not required to provide consent. If the patient does not have access to complete an electronic form, a consent will be mailed with a return envelope to receive written consent. Postage costs will be covered by the study. Once consent is obtained, the patient will received an emailed or hard copy of the signed document. Following consent, the patient will complete baseline measures (questionnaires administered electronically or by mail; accelerometers administered by mail). Following baseline measurement, patients will be randomized to intervention or wait-list control and attend their clinic visit. The study staff will call the participant one-week before their clinic visit to remind them of their appointment time, give them details about the appointment and address any barriers they may be facing to complete baseline measurements. Follow-up

St.Louis Washington University in St.Louis

FOR IRB USE ONLY \$STAMP_IRB_ID \$STAMP_APPRV_DT \$STAMP_REL_DT \$STAMP_EXP_DT

measures will be administered immediately following the clinic visit (within 48 hours) and 3-months after the clinic visit electronically and by mail. Patients will only return to the clinic for a routine visit at 3-months if it meets their standard of care based on their baseline clinical values for CVH risk. Wait-list control will be sent tailored prescriptions via the PREVENT tool following the completion of follow-up measurements. Participants will receive up to \$75 dollars in gift cards for participation. Participants will receive \$25 after baseline, \$25 after 3-month follow-up and \$25 for wearing an accelerometry device to measure their physical activity.

Patients (n=10) and their parents (n=10) who participate in focus groups will provide an additional written consent in-person prior to the start of the discussion. Consent will be administered in a single room with patients and parents. Once consent is administered, patients and parents will be divided into two private rooms to conduct separate focus groups simultaneously.

4.2.3 Provider enrollment

Following the presentation of the study at the clinic's monthly research meeting, all eligible providers will be sent electronic consent documents and provided with [name] contact information (phone and email) to ask additional questions. If consent is not received, the study team will follow-up with providers via email or phone.

4.3 Schedule of Events

4.3.1 Patient Schedule of Events

We anticipate that study participation will be between 4 and 5 months from the point of recruitment to completion (Figure 2).

Figure 2: Timeline of events for an enrolled patient.

Consent, enrollment & baseline measurement will occur electronically or via mail prior to the clinic visit. The patient will complete a written signed consent,

FOR IRB USE ONLY \$STAMP_IRB_ID \$STAMP_APPRV_DT \$STAMP_REL_DT \$STAMP_EXP_DT

complete a survey assessing their health behaviors and attitudes and wear an accelerometry device for 7 days prior to the clinic visit. Parents/legal guardians of study participants will be asked to complete a baseline demographics survey delivered electronically before the clinic visit or completed in the waiting room at the clinic visit. In addition, study staff will extract EHR data (patient demographics and CVH risk factors) and upload the most recent information into the PREVENT tool prior to the patient's clinic visit. The patient will be randomized to intervention or wait-list control.

PREVENT tool interaction (intervention). The patient will attend a routine clinic visit remotely or in-person at the Late Effects Clinic at either St. Louis Children's Hospital or the St. Louis Children's Specialty Care Center. During this visit, the provider will use PREVENT on a tablet or computer (in-person or via a teleconference call) to discuss risk, and deliver a tailored behavior change plan inclusive of patient-centered community resources. The PREVENT tool will be pre-loaded by study staff with all necessary patient information (demographics and CVH risk factors) and show the date in which these data were collected. The provider may update any patient information at the time of the visit. PREVENT uses a robust informatics approach developed by [name] (secondarymentor)³⁴⁻³⁶ to visually display Life's Simple 7 Cardiovascular Risk Factors (e.g., weight, blood pressure, inactivity) and calculate the patient's overall risk for developing cardiovascular disease. Physical activity and food intake recommendations that are tailored to the patient's current weight status and health behaviors using evidence-based recommendations (Trim Kids,³⁷ the Stoplight Diet³⁸) proven to be effective in youth are delivered to the patient. An interactive map of community resources near the patient's home will allow the patient to select resources that will support the recommended behavior change. Community resources (e.g., parks, fitness and recreation centers, farmer's markets, food pantries) were pulled from YELP using an API key. Resources were validated against lists manually generated via online searching of physical activity and food departments and organizations (e.g., the department of parks, recreation and forestry) and google. A final action plan (behavior change prescription, community resources and education) will be provided to the patient at the visit and/or electronically via email or text-message. Patient follow-up will be supported by automatic email or text-message check-ins at 4, 8 and 12 weeks. Within the 4-, 8- and 12- week email/text message check-ins the patient will be asked to answer questions about meeting their physical activity and nutrition goals. Based on the response, the patient will receive an automated email and/or text message with an updated prescription.

Wait-list control. Patients will attend a routine care visit in-person or remotely. A PREVENT action plan (behavior change prescription, community resources and education) will provided to the patient via email after the completion of follow-up measurement.

Follow-up measurement. Immediately following the clinic visit (within 48 hours) all patients will be sent electronically a brief 10-question (yes/no) survey regarding their clinical interaction. Participants randomized to intervention will also receive questions about their satisfaction with the

FOR IRB USE ONLY \$STAMP_IRB_ID \$STAMP_APPRV_DT \$STAMP_REL_DT \$STAMP_EXP_DT

PREVENT tool. Three months after the patient's clinic visit, they will be sent the Health Behavior & Attitudes Survey electronically and an accelerometer via mail. Only patients who presented with abnormal values for CVH risk factors will return to the Late Effects Clinic to complete a routine clinic visit in accordance with the standard of care for these high-risk patients. Study staff will extract the most-recent EHR data for CVH risk factors for all patients.

Qualitative data collection. Semi-structured interviews will be completed within one month of the completion of follow-up measurement for all participants that received the PREVENT tool.

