4.3.2 Provider Schedule of Events

Figure 3: Timeline of events for providers.

We anticipate that providers study participation will be approximately 11 months in duration. All providers at The Late Effects Clinic will be invited to view an online training on how to use the PREVENT tool prior to the start of patient recruitment. The online training will be recorded and disseminated to ensure that all providers are able to view the training. At this time, providers will be supplied login credentials to access the PREVENT tool. Following the training, all providers will be asked to complete the Clinical Sustainability Assessment Tool electronically. Once the intervention period begins, study staff will notify the provider if their patient was randomized to intervention to ensure that PREVENT is used during the care visit. Tablets will be available at the clinic if providers choose to use them to administer the PREVENT tool. However, the PREVENT tool can be administered via any computer or tablet using their login credentials. A subset of patient-provider interactions (n=15) may be observed and recorded while PREVENT is being used. Providers who used PREVENT will be asked to complete an electronic follow-up survey. Within one month of completing the intervention, providers will participate in in-depth interviews. Interviews will be held in-person, over the phone or using zoom technology.

FOR IRB USE ONLY \$STAMP_IRB_ID \$STAMP_APPRV_DT \$STAMP_REL_DT \$STAMP_EXP_DT

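### Control records appear to be live in PREVENT at tool-free visits, with little to keep providers from opening them and no planned by-arm check of exposure

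*Combined protocol and SAP*

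**What the plan says.** **Loading.** In section 4.3.1 the paragraph on consent, enrolment and baseline applies to all patients. It says that "study staff will extract EHR data (patient demographics and CVH risk factors) and upload the most recent information into the PREVENT tool prior to the" clinic visit, and its next sentence reads "The patient will be randomized to intervention or wait-list control". Section 4.4.1 repeats the pre-visit upload with no arm restriction, allows values to be updated inside the tool at the visit, and takes the in-tool values at that time as baseline. Section 4.4.3 uses the baseline survey of all 50 adolescents to fill the tool's risk profile. The intervention paragraph of section 4.3.1 also describes pre-loading.

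**Randomisation and access.** Section 4.2.1: "Following baseline measurement, patients will be randomized to intervention or wait-list control and attend their clinic visit". Section 4.3.2 invites all Late Effects Clinic providers to an online training before recruitment and adds: "At this time, providers will be supplied login credentials to access the PREVENT tool". It also says that "the PREVENT tool can be administered via any computer or tablet using their login credentials". Staff tell a provider when a patient is in the intervention arm, so that the tool is used.

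**Control visit and measurement.** Controls have a routine visit and receive their action plan by email only after follow-up (sections 4.2.1 and 4.3.1). Within 48 hours "all patients will be sent electronically a brief 10-question (yes/no) survey regarding their clinical interaction"; its items are not given. Observation and audio recording concern interactions in which PREVENT is used (sections 4.3.2 and 4.4.7).

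**The concern.** The Aim 2 hypothesis in section 5.1 contrasts patients who receive PREVENT at their visit with patients who do not. That contrast needs control visits to be free of the tool. If control records are already loaded and the same clinic staff can open them, some control visits may include the risk display or a plan. Section 4.4.1 even supplies a reason to open a record: updated values may be entered in the tool at the visit, and they then become the baseline.

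Contamination of this kind would usually shrink the between-arm difference. If control exposure is not reported, the reader cannot tell how far it contributed to a small difference. The pilot would also not show whether randomising individual patients within one clinic is workable, which the larger trial foreseen in section 5.2 needs to know.

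**Working it through.** **1. Are control records in the tool?** Three places point to yes: the common pre-visit paragraph of 4.3.1, the unrestricted upload in 4.4.1, and the use of the n=50 survey to fill the tool in 4.4.3. The baseline rule in 4.4.1 adds weight: section 5.2 compares change from baseline between arms, so if baseline is the in-tool value, controls must be in the tool. The pre-loading sentence under the intervention heading does not limit the other three. This is a strong inference, not an explicit statement.

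**2. What separates the arms at the visit?** Two things: notification of intervention patients, and the definition of the control visit as routine care. No section assigns providers to arms, locks control records, or tells providers to keep PREVENT closed for controls.

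**3. What would reveal exposure of controls?** The 48-hour survey reaches both arms but is not named in Table 3 or section 5.2. Observation and recording do not cover ordinary control visits. Section 6.0 stores the tool's data but describes no review by arm.

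**4. How sensitive is the comparison?** The plan gives N = 50 ("Fifty adolescents aged 12 to 19 years at risk for poor CVH") without a power calculation, effect size or SD, so there is no figure to reproduce. The following is illustration only.

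Assumptions: 1:1 allocation, 25 per arm with complete data; SD = 1; two-sided alpha 0.05 (section 5.2 gives p<0.05 without sidedness); a share c of controls is exposed and receives the full effect.

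- Difference detectable with 80% power: (1.960 + 0.842) × √(2/25) = 0.792 SD.
- Difference left after contamination: 0.792 × (1 − c).
- Power: Φ(0.792 × (1 − c) / √(2/25) − 1.960).
- Total N to hold 80% power: 2 × 25/(1 − c)², rounded up per arm.

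| c | Controls exposed (c × 25) | Remaining difference (SD) | Power | Total N for 80% |
|---|---|---|---|---|
| 0 | 0 | 0.792 | 80% | 50 |
| 10% | 2.5 | 0.713 | 71% | 62 |
| 20% | 5 | 0.634 | 61% | 80 |
| 30% | 7.5 | 0.555 | 50% | 104 |
| 50% | 12.5 | 0.396 | 29% | 200 |

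No value of c comes from the documents. If an opened record delivers only a fraction f of the effect, the factor is 1 − c × f: with c = 20% and f = 0.5 it is 1 − 0.10 = 0.90, the 10% row.

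**The case against.** The strongest reply is that the plan already separates the arms. Use of PREVENT is prompted by arm, the control visit is defined as routine care, and the plan goes to controls only after follow-up. The both-arm survey asks about the clinical interaction and may already contain the needed items. Section 5.2 refers to survey data in general terms that could include it. The background section says providers lack time for tailored care, which makes unprompted use less likely. All of this stands, and it rules out several stronger readings:

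- A reader might infer that nothing prevents or measures contamination. The notification and routine-visit rules give some separation, and the survey could measure exposure.
- A reader might take it as stated that every control is loaded, that every provider holds a login and that each sees both arms. The first is inferred; providers are invited to the training at which logins are supplied; patient-provider assignment is not described.
- A reader might infer that a finished prescription and resource map await each control. The text loads patient information; the provider delivers the plan, and the patient selects resources at the visit. The 4-, 8- and 12-week check-ins are also part of the intervention. Full effect in an exposed control is therefore an upper bound.
- A reader might infer that contamination alone would make a null result uninterpretable. With 50 patients and no power calculation, a null result would not show the tool ineffective even without contamination.

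A second objection concerns the remedy. If only intervention patients are loaded and section 4.4.1 stays as it is, intervention baselines come from the tool, with possible visit-day updates, and control baselines from an earlier EHR extract. That would affect BMI, the primary health outcome. The objection is correct, so the remedy must also set one baseline rule for both arms.

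**Conclusion.** The point holds as a low-cost design improvement that should be made. Followed as written, the plan appears to leave control records live in PREVENT at visits meant to be tool-free and gives a reason to open them. Its separation of the arms is weak, and it specifies no by-arm report of exposure. The direction of any bias would usually be toward no difference. Its size cannot be estimated: the table shows sensitivity under assumed exposure rates, full effect and 25 per arm, not an expected loss. The conclusion rests on reading the uploads in sections 4.3.1, 4.4.1 and 4.4.3 as covering both arms. If controls are in fact not loaded, the baseline rule in 4.4.1 cannot apply to them, and that rule needs correcting in any case.

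**What to change.** 1. Sections 4.3.1 and 4.4.1: before the visit, upload or unlock a PREVENT record only after randomisation and only for intervention patients. Create wait-list profiles once their 3-month measures are complete, when their plan is due.
2. Section 4.4.1: define baseline CVH values, including BMI, by one rule for both arms: the most recent EHR value up to and including the visit, not the value in the tool. Changes 1 and 2 must be made together.
3. Section 4.3.2: also tell providers which study patients are wait-list, and that PREVENT is not to be opened at those visits.
4. Section 4.3.1, follow-up measurement, and section 5.2: make sure the 48-hour survey asks both arms whether a risk display, a behaviour plan or a community-resource map was shown, and report the answers by arm.

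The cost is a small re-ordering of staff tasks, one instruction to providers and possibly one or two yes/no items in an existing survey. No visits or patients are added. Counselling habits that providers carry over from the training would be measured only in part and not prevented.

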4.4 Data Collection Methods

Theoretical underpinnings. This feasibility study will apply principles of Designing for Dissemination, Implementation and Sustainability (D4DIS) to understand factors critical to external validity and refine the existing PREVENT tool to fit well with provider's and patient's needs, assets and timeframes.³⁹ We seek to speed translation of the PREVENT tool into practice by simultaneously collecting mixed method data regarding determinants of current and future implementation of the PREVENT tool, guided by the new Reach, Efficacy, Adoption, Implementation, and Maintenance (RE-AIM) framework.^{40,41} The updated RE-AIM framework will be used to identify barriers to implementation and dissemination as outlined in **Table 3**.

RE-AIM Construct	Measure	Data Source	Stakeholder
Reach	Representativeness compared to eligible clinic population	EHR data; Demographics survey	Patients
Efficacy	Changes in health behaviors and attitudes; Change in CVH risk factors	Health Behavior & Attitudes Survey; accelerometry; EHR data	Patients
Adoption	Usability; acceptability; consistency with priorities/values	Patient and parent interviews; Provider survey	Patient, parent, provider
Implementation	Intervention delivery; fidelity to the protocol; time of PREVENT use; compatibility with workflow	Direct observation, audio recordings of implementation	Patient
Maintenance	Barriers and enabling factors for continued implementation of PREVENT	Qualitative interviews; Provider survey; Clinical Sustainability Assessment Tool	Provider

Table 3: RE-AIM Outcome Measures

4.4.1 EHR data extraction. Patient demographics (e.g., sex, date of birth, race/ethnicity) and the most recent risk factors for CVH (height, weight, fasting blood glucose, total cholesterol, blood pressure, smoking status) will be extracted at baseline (prior to clinic visit) and at follow-up (3-months). Available EHR data will be uploaded into PREVENT prior to the clinic visit but may be updated within the PREVENT tool at the time of the clinic visit if updated values are attained. CVH risk factor data within the tool at the time of the clinic will be used as baseline values and used to determine changes from baseline to follow-up. Only patients with abnormal baseline values will return for a follow-up clinic visit at 3-months. Therefore, we acknowledge that not all patients will have updated

FOR IRB USE ONLY \$STAMP_IRB_ID \$STAMP_APPRV_DT \$STAMP_REL_DT \$STAMP_EXP_DT

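### The 3-month BMI value need not have been measured after the clinic visit, and Section 5.2 does not say how values that were never updated enter the change analysis

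*Combined protocol and SAP*

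**What the plan says.** Section 4.4.1 chooses BMI as the primary health outcome because height and weight are expected to be the items most often on file at both time points. The CVH risk factors "will be extracted at baseline (prior to clinic visit) and at follow-up (3-months").

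Baseline: the latest record is loaded into the tool before the visit, values "may be updated within the PREVENT tool at the time of the clinic visit if updated values are attained", and then "CVH risk factor data within the tool at the time of the clinic will be used as baseline values" (4.4.1).

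Follow-up: "Study staff will extract the most-recent EHR data for CVH risk factors for all patients" (4.3.1, Follow-up measurement).

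Who is seen again: under 4.2.1, patients come back at 3 months only "if it meets their standard of care based on their baseline clinical values for CVH risk". Section 4.3.1 says "Only patients who presented with abnormal values for CVH risk factors will return to the Late Effects Clinic", and 4.4.1 says "Only patients with abnormal baseline values will return for a follow-up clinic visit at 3-months". Section 4.4.1 goes on: "Therefore, we acknowledge that not all patients will have updated" BMI, glucose, cholesterol and blood pressure. It adds that finding out which data can be had is a purpose of the study. In both arms the index visit may be in person or remote (4.3.1).

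Analysis: Section 5.2 compares change from baseline between arms by linear regression at p<0.05. It has no rule for values that are missing or were not updated.

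**The concern.** The 3-month label dates the extraction, not the measurement. A patient who does not return still has a latest value on the chart, and it may be the one already used as baseline. In that case the recorded change is exactly zero, whatever happened to the patient. There is a second route. If a height and weight are taken at the index visit but not entered in the tool, that reading becomes the latest one on file and can stand as follow-up, although it was taken before PREVENT could have had any effect.

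One analyst could follow 4.3.1 literally and keep such values. Another could follow the sense of 4.4.1 and drop them. They would report different BMI results from the same data. At stake are the size and apparent precision of the BMI contrast, and also the availability question in 4.4.1: without measurement dates, a refreshed value cannot be told from an old one.

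**Working it through.** The plan gives no effect size, SD, power or return fraction, so there is no figure of its own to reproduce.

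**Text check.** Section 4.3.1 names the source (the latest value, for everyone), 4.4.1 gives the extraction time, and 5.2 gives the model. None gives an earliest permissible measurement date or a window, and 5.2 does not say whether an old value is missing or a zero change.

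**Inputs.** From the documents: 50 patients (2.0, 3.0) and p<0.05 (5.2). Assumed: 25 per arm, two-sided testing, SD of change 1, mean control change 0, true effect d = 0.5 SD, and the same share f with a post-visit value in each arm.

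**Old values kept as zero change.**
- Expected difference = f × d.
- Variance of recorded change = f in controls and f + f(1−f)d² in the intervention arm.
- SE = √[(sum of the two variances)/25].
- Example, f = 0.5: difference = 0.5 × 0.5 = 0.25; variances 0.5 and 0.5 + 0.25 × 0.25 = 0.5625; SE = √(1.0625/25) = 0.206. With all 50 truly re-measured, SE = √(2/25) = 0.283.

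**Old values coded missing.** Expected difference = d and SE = √[2/(25f)]. At f = 0.5, SE = √(2/12.5) = 0.400.

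Coverage, interval width and power below are from 40,000 simulated trials per setting with a pooled two-sample t interval. Coverage is of the effect in the whole cohort, here 0.5.

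| f | 0.3 | 0.5 | 0.7 | 0.9 | 1.0 |
|---|---|---|---|---|---|
| Kept: estimate | 0.15 | 0.25 | 0.35 | 0.45 | 0.50 |
| Kept: coverage | 42% | 75% | 90% | 95% | 95% |
| Kept: width | 0.64 | 0.82 | 0.96 | 1.08 | 1.13 |
| Kept: power | 14% | 22% | 30% | 37% | 41% |
| Missing: patients analysed | 15 | 25 | 35 | 45 | 50 |
| Missing: estimate | 0.50 | 0.50 | 0.50 | 0.50 | 0.50 |
| Missing: width | 2.32 | 1.67 | 1.38 | 1.20 | 1.13 |
| Missing: power | 14% | 22% | 30% | 37% | 41% |

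Coverage with old values coded missing is 95% throughout. A larger assumed effect dilutes in the same way: with d = 0.8 and f = 0.8 / 0.6 / 0.4, keeping old values gives 0.64 / 0.48 / 0.32 with coverage 90 / 71 / 33%.

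**Why power is the same.** Ignoring the small f(1−f)d² term, the ratio of difference to SE is f × d / √(2f/25) = d√(25f/2) with old values kept. With them missing it is d / √[2/(25f)] = d√(25f/2). With no true effect, false positives under the first rule are 4.6 to 5.0%.

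**When patients not re-measured respond differently.** If their effect is e, the cohort effect is f × d + (1−f) × e, and keeping old values falls short by (1−f) × e.
- e = 0.25: at f = 0.5 the cohort effect is 0.25 + 0.125 = 0.375 against an estimate of 0.25. Coverage at f = 0.3 / 0.5 / 0.7 is 76 / 89 / 94%.
- e = 0: no shortfall, and coverage is 95%.

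**The case against.** The strongest reply is that the harmful reading fits the text least. If an old reading counted as a 3-month value, nearly every patient with a baseline value would have one. The remarks in 4.4.1 about incomplete updating and data availability would then mean little. On this view, extracting for every patient says whose charts are searched, not how an old value is analysed. This stands as the likelier intention, and a reader should not infer that the plan will score old values as zero change; no passage says so. But an acknowledgement is not an analysis rule, and 5.2 supplies none.

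Second, the p<0.05 test is the only inference 5.2 specifies, and it hardly changes. This also stands. Section 5.2 promises no confidence interval, so the coverage figures describe the precision anyone would attach to the estimate, not a planned output.

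Third, return may be nearly complete. Criterion 5 in 3.1 requires BMI at or above the 85th percentile. If that counts as abnormal, every patient would return and the problem almost disappears. Section 4.4.1 expects otherwise, but nothing supports a particular fraction such as 0.3 or 0.5.

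A reader might also infer a spurious benefit, because providers are told only about intervention patients (4.3.2) and baselines might therefore be fresher in that arm. The documents do not support this as a finding. The upload and baseline rules apply to all patients, the notice concerns use of PREVENT and not data entry, and nothing indicates how many controls would be affected or by how much. It is a reason for one explicit baseline rule and no more.

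**Conclusion.** The gap is real and should be closed before extraction. The primary health outcome has a follow-up value with no required measurement date, and the analysis section does not settle what an old value means. If old values were kept, the contrast would be diluted by the share re-measured and its precision overstated, unless patients not re-measured had no effect. The harm is not lost power or a spurious benefit, given the same baseline rule and similar return in both arms.

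The size is open. On the assumptions above it runs from negligible at nine in ten re-measured to a halved estimate at one in two. Allocation, SD, effect and return fraction are all assumed.

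Two further inferences go too far. One is that a diluted BMI estimate would set the design of the larger trial: 5.2 says only that the integrated data will inform an implementation strategy for it. The other is that coding old values as missing gives a sound estimate without conditions. That comparison relies on similar return in the two arms and speaks only for patients selected on abnormal baselines.

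**What to change.** In 4.3.1 and 4.4.1:
- Record the measurement date of every extracted value, at baseline and follow-up.
- Count a follow-up value only if it is later than the clinic visit and falls in a window around 3 months that the study team sets in advance.
- Apply one baseline rule in both arms, for example the latest chart value up to and including the clinic visit.
- Reconcile the term abnormal values with criterion 5 in 3.1, so that the expected number of returning patients can be stated.

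In 5.2:
- State that a patient without an in-window value is missing, not unchanged.
- Report the number with an in-window value by arm as a feasibility result.
- Limit the BMI conclusion from chart data to those patients, and note that the comparison relies on similar return in the two arms.

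The cost is some wording, one date field per value and a filter, with no extra visits. The tool already shows collection dates for pre-loaded data (4.3.1); follow-up dates would have to be added to the extraction. The price is fewer analysable values: at an assumed f = 0.5, about 25 of 50, with interval width 1.67 against 1.13 if all were re-measured. The subset is selected on abnormal baselines and need not represent the rest (0.50 against a cohort effect of 0.375 in the half-effect case). There is no gain in power.
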